1.0 Objectives*

- 1.1 This study aims to investigate the effect of abobotulinum toxin A on the symptoms of Raynaud's phenomenon. By studying the effect of abobotulinum toxin A on Raynaud's symptoms among a more diverse population we hope to provide insight into the patients most likely to benefit from abobotulinum toxin A.
- 1.2 Our hypothesis is that hands that receive injections of abobotulinum toxin A will experience greater relief from symptoms compared to hands which do not

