9.0 Procedures Involved*

9.1 Our study is a double-blind randomized placebo-controlled trial.

- Treatment arm: Injection of 300 units of abobotulinum toxin A in 10 ml of non-bacteriostatic normal saline to chosen hand.
- Control arm: Injection of 10 ml of non-bacteriostatic normal saline to chosen hand.
- Randomization will be determined by coin flip as follows:
 - Heads: Right hand – treatment arm; Left hand – control arm.
 - Tails: Right hand – control arm; Left hand – treatment arm.

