11.0 Data Management* and Confidentiality

11.1 The data will be analyzed for significant differences with aid of a statistician. A significance level of 0.05 will be used for statistical hypothesis testing. The results of the data analysis will be graphed for each parameter.

- Categorical variables, such as sex (male and female), age, and comorbidities (e.g., scleroderma) will be reported descriptively, as frequencies and percentages. Outcomes in this study are visual analog scale for pain (VAS Pain), Raynaud's Condition Score (RCS), and the Disabilities of the Arm, Shoulder and Hand Score (QuickDASH), which are continuous variables. In addition, the number of digital ulcers and number of attacks/episodes per week, which are discrete variables, will be measured as outcomes. These continuous and discrete variables will be expressed as mean \pm standard deviation, with standard error of the mean (SEM).
- To assess between group differences, an Independent samples t-tests will be conducted separately for the three time periods: baseline, 1-month, and 3-month. Additionally, a dependent sample t-test will be used to assess within-group differences from 1-month to 3-month, separately for the experimental and control groups. It is possible to use the baseline measurement as a covariate in an analysis of covariance (ANCOVA) and/or in a repeated measures ANOVA. Thus, the researchers will also explore these additional analyses if the sample size permits.
- All tests will be two-sided, and p-values < 0.05 will be considered statistically significant. Statistical analyses will be conducted using SPSS 24.0 (IBM; Chicago, IL).

PROTOCOL TITLE: The Effect of Abobotulinum Toxin A on the Symptoms of Raynaud's Phenomenon, a Double-Blind Randomized Placebo-Controlled Trial

11.2 Utilizing the statistical software G*Power it was determined that 16 patients would be needed to detect a 2-point difference in the RCS among the treatment arms. (G*Power) This assumes a standard deviation of 1.92, power of 0.8, alpha of 0.05, and effect size (d) of 1.04. (Merkel)

11.3 Data will be managed as follows:

- Data will be stored in the secure HIPAA-compliant database called REDCap.
- Unique identifiers will be created using sequential numbers (i.e. 1, 2, 4 etc.).
- No data collection instrument in REDCap will contain identifying information

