12.0 Provisions to Monitor the Data to Ensure the Safety of Subjects*

12.1 The plan to periodically evaluate the data collected regarding both harms and benefits to determine whether subjects remain safe is as follows:

- The principal investigator and statistician will review cumulative VAS Pain scores, RCS data, QuickDASH, number of digital ulcers, and number of attacks/episodes per week data at the halfway point (8 subjects).
- If any of the change in VAS Pain scores, RCS, QuickDASH, number of digital ulcers, or number of attacks/episodes per week for the treatment should become statistically significantly worse than the control with a $p < 0.05$ then the study will be suspended immediately.
- Alternatively, if the change in VAS Pain scores, RCS, QuickDASH, number of digital ulcers and number of attacks/episodes per week for the treatment should become statistically significantly better than the control with a $p < 0.05$ then the study will also be suspended immediately.

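### Section 11.1 commits only to unadjusted independent-samples t-tests between arms; where outcomes are recorded per hand, the baseline-adjusted hand difference should be the committed analysis

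*Combined protocol and SAP*

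**What the plan says.** Section 1.2 states the hypothesis as a comparison of hands: "hands that receive injections of abobotulinum toxin A will experience greater relief from symptoms compared to hands which do not". Section 9.1 allocates within the patient: "Randomization will be determined by coin flip as follows", after which one hand receives active treatment and the other saline.

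Section 11.1 then sets out three things:
- Between arms: "To assess between group differences, an Independent samples t-tests will be conducted separately for the three time periods: baseline, 1-month, and 3-month".
- Within arms: "a dependent sample t-test will be used to assess within-group differences from 1-month to 3-month, separately for the experimental and control groups".
- Use of baseline as a covariate, or a repeated measures ANOVA, is described as possible: "Thus, the researchers will also explore these additional analyses if the sample size permits". No time points are named, and the text does not say how the two hands of one patient would enter the model.

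Section 11.2 sizes the trial on RCS: "16 patients would be needed to detect a 2-point difference in the RCS among the treatment arms", with SD 1.92, d = 1.04, alpha 0.05 and power 0.8.

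The timeline in 9.2 schedules outcome visits at 1, 3, 6 and 12 months. Section 9.4 lists the outcomes but does not say which are recorded separately for each hand.

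**The concern.** The design gives two sources of precision at no extra cost: each patient is his or her own control, and both hands are assessed before injection. The committed tests use neither. An independent-samples test treats 32 hands as 32 unrelated units, and the follow-up tests ignore the starting values.

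One of the three committed between-arm tests is at baseline. Allocation is by coin flip, so any difference there is chance, and the test says nothing about hypothesis 1.2.

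The condition attached to ANCOVA gives no decision rule. The planned number is already fixed at 16 patients, and adjusting the hand difference for baseline costs one degree of freedom. As written, the choice can be made after the data are seen. With 16 patients, interval width matters: the difference sought is 2 points, and the planned half-width is about 1.4.

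**Working it through.** **Inputs from the documents.** Target difference 2 RCS points, SD 1.92, d = 1.04, two-sided alpha 0.05 and 16 patients (11.1 and 11.2); one hand per arm in each patient (9.1), so 16 hands per arm.

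**Assumptions, because the documents do not give them.** 1.92 is taken as the per-hand SD at a visit. The between-hand correlation is ρ, shown at 0 and 0.5. The correlation between the baseline and follow-up hand differences is r, shown from 0 to 0.7.

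**Step 1: the plan's own figure.** d = 2/1.92 = 1.04. A two-sample, two-sided t-test with 16 hands per arm (30 df) has power 0.812; 15 per arm gives 0.785. The stated 16 reproduces.

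**Step 2: planned interval.** Half-width = t(30) × SD × √(2/n) = 2.042 × 1.92 × √(2/16) = 1.386 points.

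**Step 3: paired, unadjusted.** SD of the hand difference = 1.92 × √(2(1−ρ)), which is 2.715 at ρ = 0 and 1.92 at ρ = 0.5. Half-width = t(15) × SD/√16, with t(15) = 2.131:
- ρ = 0: 2.131 × 2.715/4 = 1.447
- ρ = 0.5: 2.131 × 1.92/4 = 1.023

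**Step 4: paired and baseline-adjusted.** Regress the follow-up hand difference on the baseline hand difference and estimate the intercept. Relative to step 3, the variance is multiplied by (1−r²)(1 + 1/(n−3)) = (1−r²)(1 + 1/13), and t(14)/t(15) = 1.0063. The CI ratio is 1.0063 × √[(1−r²)(14/13)].

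| r | Variance factor | CI ratio to unadjusted paired | Half-width, ρ = 0 | Half-width, ρ = 0.5 |
|---|---|---|---|---|
| 0 | 1.077 | 1.044 | 1.511 | 1.068 |
| 0.3 | 0.980 | 0.996 | 1.441 | 1.019 |
| 0.5 | 0.808 | 0.904 | 1.308 | 0.925 |
| 0.7 | 0.549 | 0.746 | 1.079 | 0.763 |

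A simulation of the intercept test (40,000 runs) gave variance ratios of 1.078, 0.977, 0.805 and 0.546, and type I error of 4.9% to 5.1%.

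**Step 5: break-even points.**
- Against the unadjusted paired interval, the ratio equals 1 at r = 0.288.
- Against the planned interval at ρ = 0, the adjusted half-width equals 1.386 at r of about 0.40. At ρ = 0 and r = 0 it is 1.511/1.386 = 1.09, about 9% wider.

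**Step 6: where the gain comes from at ρ = 0.5.** Pairing takes 1.386 to 1.023 (ratio 0.74). Adjustment then changes 1.023 to between 1.068 (r = 0) and 0.763 (r = 0.7). Most of the gain is from pairing.

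**The case against.** The strongest reply is that nothing committed in 11.1 is invalid. The arm means are compared directly at 1 and 3 months, the sample size matches the test named, and ANCOVA is already mentioned. The correlations that decide whether adjustment helps are in no document, and at r = 0.3 adjustment makes almost no difference to a paired interval. This stands, and it limits the point to a cheap gain in precision. It does not defend leaving the choice open, because the condition on sample size has no threshold.

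A second reply is that the proposed analysis needs outcomes recorded per hand. The available text does not confirm this, and the case report forms are attachments not seen here. That also stands, so the fix is conditional on it.

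Three stronger readings are tempting, and the documents do not support them.
- A reader might infer that months 6 and 12 were left out of 11.1 in error. Section 11.1 tests at 1 and 3 months, and the administration text in 9.2 also refers to evaluation at 1 and 3 months, so a deliberate three-month efficacy window is plausible. Scheduling a visit does not oblige a test there. Section 11.1 also promises summaries and graphs, and the optional repeated measures ANOVA could include the later visits. What is missing is a statement of their status. The comparison of change in 12.1 does not supply it, since it is a suspension rule at the halfway review.
- A reader might infer that the within-arm tests from 1 to 3 months will be read as treatment effects. The protocol does not say so, and it commits to direct between-arm tests at both visits.
- A reader might infer that the planned comparison is biased or the trial mis-sized. Neither follows: the estimate is the same difference in means, and 16 reproduces.

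**Conclusion.** The point holds as a worthwhile, inexpensive improvement to the committed analysis; it does not show that the planned test is wrong. If the hands of a patient are moderately correlated (0.5 assumed), the RCS half-width falls from 1.39 points to between 1.07 and 0.76 for r from 0 to 0.7, mostly through pairing. If the hands are uncorrelated, the adjusted analysis is less precise than the planned test unless r exceeds about 0.40. The size therefore rests on two correlations that the documents do not give, on reading 1.92 as a per-hand SD, and on RCS being recorded per hand. The status of the 6- and 12-month visits and the labelling of the within-arm tests are minor clarifications.

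**What to change.** First confirm on the case report forms which outcomes are recorded separately for each hand. Then amend 11.1 as follows:

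1. For RCS, the outcome used for sizing, at one named visit: regress the treated-minus-control hand difference on the baseline hand difference, and test the intercept with a 95% CI. Leave the baseline difference uncentred, so that the intercept refers to hands that start equal; centring at the sample mean would simply return the unadjusted difference.
2. If RCS is not recorded per hand, say that this analysis cannot be applied to it.
3. Report the same estimate as secondary at the other visits, including 6 and 12 months, and for the other continuous outcomes recorded per hand.
4. For ulcer and attack counts, use a method suited to paired counts, or report them descriptively.
5. Drop the baseline significance test.
6. Add one sentence stating that the within-arm tests from 1 to 3 months are descriptive.

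The cost is SAP wording and modest analysis work on data already scheduled, with no new visits or patients. The statistical price is one degree of freedom. The interval is about 4% wider than an unadjusted paired one if r = 0 (break-even about 0.29), and about 9% wider than the planned test if both correlations are 0.

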13.0 Withdrawal of Subjects*

13.1 Subjects will be withdrawn from the research without their consent if they become intolerant to the treatment and/or the researchers determine that they are too nervous, anxious to continue.

13.2 Orderly termination will proceed at the end of study period for all subjects. This will simply mean no further visits and no further data collection will occur.

13.3 Subjects may voluntarily terminate their participation in the research at any time by informing a member of the research team. A subject may partially withdraw from the study after the initial treatment and control have been administered or even during administration if the participant is unable or unwilling to continue or do the follow up visits.

If a subject withdraws or is withdrawn from the study prior to completion, further data collection will be stopped. However, partial data already collected will be used for analysis.

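### Section 13.3 says partial data will be used, but the cross-visit analyses in 11.1 drop any subject with a missing visit and no missing-data method is named

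*Combined protocol and SAP*

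**What the plan says.** Each patient supplies both hands, allocated by coin flip (9.1: "Heads: Right hand – treatment arm; Left hand – control arm", and the reverse for tails).

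Section 11.1 commits to two kinds of test:

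- independent-samples t-tests between treated and control hands, run separately at baseline, 1 month and 3 months;
- a dependent t-test of the change from 1 to 3 months, within each group.

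It then adds an option: "It is possible to use the baseline measurement as a covariate in an analysis of covariance (ANCOVA) and/or in a repeated measures ANOVA". The next sentence makes these analyses exploratory and conditional on having enough subjects. On software it says "Statistical analyses will be conducted using SPSS 24.0", without naming a procedure.

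Section 13.3 stops data collection at withdrawal but adds that "partial data already collected will be used for analysis". No section states an analysis set, a method for missing visits or an expected dropout rate. Section 20.2 speaks of 20 enrolled so that 16 complete, whereas 4.1 and 23.2 describe the 16 as subjects who pass screening.

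**The concern.** Section 13.3 states an intention and 11.1 gives no means of carrying it out across visits. A classical repeated measures ANOVA needs a value at every visit in the model and removes the whole subject when one is absent. The dependent t-test likewise needs both the 1-month and the 3-month value. A subject who attends at 1 month and then leaves adds nothing to either.

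The 3-month between-hand t-test has a related weakness. It is computed on those who remain and ignores what the leavers showed at 1 month. Sections 8.2 and 13.1 link some withdrawals to reactions or intolerance, so loss completely at random cannot be taken for granted. If leaving is related to the toxin-minus-saline difference already seen, the 3-month result describes a selected group. With 16 patients, a few such losses matter.

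**Working it through.** **1. The plan's own figure.** Section 11.2 says "16 patients would be needed to detect a 2-point difference in the RCS among the treatment arms", and "This assumes a standard deviation of 1.92, power of 0.8, alpha of 0.05, and effect size (d) of 1.04". Check: d = 2/1.92 = 1.04. The two-sided normal approximation gives n per arm = 2 × (1.960 + 0.842)² / 1.0417² = 14.5, rounded up to 15. The exact two-sample t-test has power 78.5% at 15 per arm and 81.2% at 16. One treated and one control hand per patient makes 16 per arm equal to 16 patients. The figure reproduces, and it rests on a two-group comparison at a single visit, not on a repeated measures ANOVA.

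**2. Which analysis uses whom.** Take a subject who attends baseline and 1 month and then leaves.

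| Analysis in 11.1 | Status | Uses this subject? |
|---|---|---|
| t-test at baseline | committed | yes |
| t-test at 1 month | committed | yes |
| t-test at 3 months | committed | no |
| dependent t-test, 1 to 3 months | committed | no |
| classical repeated measures ANOVA | optional | no, at any visit |

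**3. Loss of numbers.** The rates are assumed, since the plan gives none. If each follow-up visit is missed independently with probability p and baseline is complete, one visit has 16(1 − p) subjects and both visits are present for 16(1 − p)².

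| p | Seen at a given visit | Complete at 1 and 3 months |
|---|---|---|
| 5% | 15.2 | 14.4 |
| 10% | 14.4 | 13.0 |
| 15% | 13.6 | 11.6 |
| 20% | 12.8 | 10.2 |

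The extra loss from deleting whole subjects is about 1 to 3 of 16. If missing visits arise only from withdrawal, which is what 13.3 describes, those complete at both visits are exactly those seen at 3 months, and the ANOVA loses nobody further there. For the effect on precision alone, two-sample power at d = 1.04 is 81% with 16 patients, 75% with 14 and 68% with 12.

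**4. Possible bias.** Assumptions: true toxin-minus-saline difference 2.00 at both visits; SD of the within-patient difference 1.92; correlation of that difference between visits 0.5. The 1.92 is the plan's SD for single values. It is also the SD of the difference when the two hands correlate at 0.5, because 1.92 × √(2 × (1 − 0.5)) = 1.92.

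Suppose the 4 subjects with the smallest 1-month differences leave before 3 months. The upper 12 of 16 normal values average about 0.40 SD above the mean, so:

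- completers at 1 month: 2.00 + 0.40 × 1.92 = 2.77;
- completers at 3 months: 2.00 + 0.5 × 0.77 = 2.385, that is 2.38 to 2.39 in simulation.

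If 2 leave, the values are 2.42 and 2.21. The committed 1-month t-test uses all 16 and stays at 2.00. If leaving is unrelated to the within-patient difference, completers give 2.00 at both visits.

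**5. What a likelihood-based model does.** It carries the leavers' 1-month values into the 3-month estimate through the correlation: 2.385 + 0.5 × (2.00 − 2.77) = 2.00. Under these assumptions it gives 2.00 at both visits.

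**The case against.** The other side has a good deal to say, and most of it stands.

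- A reader might infer that 11.1 contradicts 13.3. It does not. Visit-by-visit t-tests use whatever was collected at each visit, and their subject sets differ because partial data are used.
- A reader might infer that the ANOVA is the plan's only longitudinal analysis, and that its deletions distort the trial's main result. The dependent t-test is also longitudinal, and ANCOVA would link baseline to follow-up. The ANOVA is optional, and the planned sample size does not depend on it.
- A reader might infer that the 1-month effect will be overstated. The 2.77 arises only in the optional ANOVA.
- A reader might take bias as established. Sections 8.2 and 13.1 concern reactions, intolerance and anxiety; neither ties leaving to least benefit. A withdrawal also removes one treated and one control hand together, which limits imbalance between arms.
- A reader might extend the loss calculation to all four follow-up visits. The tests in 11.1 cover baseline, 1 month and 3 months only.

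What the objection does not remove: pairing of hands gives no protection when leaving depends on the difference between the hands, the 3-month exposure affects a committed test, and the plan is silent on missing data.

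**Conclusion.** The concern holds as a gap in specification. The plan intends to use partial data, but its cross-visit analyses discard subjects with a missing visit, and nothing says how missing visits are handled. At 1 month the committed test is unaffected by later withdrawal. At 3 months the committed t-test and the optional ANOVA are both limited to subjects still present. That can bias the estimate if leaving depends on earlier outcome, and otherwise costs only precision.

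The size cannot be fixed from the documents. About 2.39 against 2.00 (4 leavers of 16) or 2.21 (2 leavers) illustrates an unfavourable, strictly selective pattern. These figures rest on the assumed SD of the difference, the between-visit correlation of 0.5 and the assumed leaving rule; they are not a forecast. Whether there is slack for dropout depends on which reading of 16 applies: subjects completing (20.2) or subjects eligible (4.1, 23.2). Under the second, nothing is set aside. The change is worth making because it is cheap.

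**What to change.** In 11.1, replace the optional repeated measures ANOVA with a linear mixed model, run with the MIXED procedure in SPSS:

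- outcomes: VAS Pain, RCS and any other continuous outcome scored per hand;
- data: every 1- and 3-month hand-by-visit value collected, including those from subjects who later leave;
- fixed effects: treatment, visit and treatment-by-visit, with the baseline value as covariate;
- random effects: patient, and hand within patient. The second carries 1-month information on the between-hand difference into the 3-month contrast.

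Report the 1- and 3-month toxin-minus-saline contrasts from this model, and state how they stand relative to the per-visit t-tests. Use a count-model analogue for digital ulcers and weekly attacks. State the analysis set, and refer to this model in 13.3 as the way partial data are used.

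Cost: SAP wording and a different procedure in the software already named; no extra data or patients. The model assumes that missingness depends only on observed values, which is weaker than what a completers-only analysis needs but cannot be verified. Subjects with baseline data only still do not contribute to the contrasts, so 13.3 should say so.

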randomized control trial seeks to compare a single formulation of BoNT, abobotulinum toxin A (Dysport), to a placebo saline group, studying the effect of BoNT on Raynaud's symptoms among a more diverse population to provide insight into the patients most likely to benefit from BoNT. Additionally, we hope that if we have positive findings that this data could be used to justify insurance coverage of BoNT in Raynaud's phenomenon. With BoNT costing hundreds to thousands of dollars per treatment, it can prove a financial burden for patients relying on BoNT for relief from symptoms and prevention of amputation.¹⁴ Preliminary findings from this study could be used to justify further studies for a new indication for Raynaud's phenomenon thus improving patients' chances for coverage and ease of access.

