8.0 Study Endpoints*

8.1 Primary endpoints: Participation in the study will end 12 months after the baseline visit or if the patient elects to be removed from the study, whichever comes first.

PROTOCOL TITLE: The Effect of Abobotulinum Toxin A on the Symptoms of Raynaud's Phenomenon, a Double-Blind Randomized Placebo-Controlled Trial

- 8.2 Primary and secondary safety endpoints: adverse reaction to the abobotulinum toxin A solution. If a participant develops a reaction, he or she will be given the option to withdraw but will not be required to withdraw, unless life threatening.

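### No efficacy outcome or visit is named as primary, and up to ten between-hand comparisons can each be called significant at an unadjusted 0.05

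*Combined protocol and SAP*

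**What the plan says.** - **Section 8.1** is headed as giving the primary endpoints, but its content is the end of follow-up: "Primary endpoints: Participation in the study will end 12 months after the baseline visit" (or at withdrawal, if earlier). Section 8.2 adds only safety: "Primary and secondary safety endpoints: adverse reaction to the abobotulinum toxin A solution".
- **Section 11.1** introduces the efficacy variables without ranking them: "Outcomes in this study are visual analog scale for pain (VAS Pain), Raynaud's Condition Score (RCS), and the Disabilities of the Arm"; the last of these three is QuickDASH. Two counts follow, digital ulcers and weekly attacks. That makes five outcomes.
- **Section 11.1** then plans that "an Independent samples t-tests will be conducted separately for the three time periods: baseline, 1-month, and 3-month". It adds within-group tests from 1 to 3 months, and ANCOVA or repeated-measures ANOVA as possible further analyses.
- **Section 11.1** closes with one rule for all of these: "All tests will be two-sided, and p-values < 0.05 will be considered statistically significant".
- **Section 11.2** bases the sample size on one outcome: "16 patients would be needed to detect a 2-point difference in the RCS among the treatment arms". It does not call RCS primary and gives no visit.
- **Section 12.1** has the investigator and statistician review all five outcomes, ending with "number of attacks/episodes per week data at the halfway point (8 subjects"), and compares the hands at p<0.05.
- **Section 2.3** sets out the intended use of the results: "Preliminary findings from this study could be used to justify further studies for a new indication". It also hopes that positive data could support insurance coverage.

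**The concern.** The hypothesis in section 1.2 is that treated hands get more symptom relief, with no measure and no time point. A reader would look to section 8 or 11.1 to learn which comparison tests it, and neither says. Under the rule in 11.1, a difference on pain, RCS, QuickDASH, ulcers or attacks, at 1 month or at 3 months, may be reported as statistically significant on equal terms. No hierarchy, adjustment or primary visit limits this.

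Two things are at stake. The first is the overall false-positive rate across the set of tests. The second is interpretation: if one of ten comparisons falls below 0.05, nobody can tell from the plan whether it was the intended test or the most favourable of several. That matters for a trial whose results are meant to support further studies and possibly coverage.

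**Working it through.** **1. The plan's own sample size reproduces.** Inputs from 11.2: difference 2, SD 1.92, power 0.80, alpha 0.05, d = 1.04 (2/1.92 = 1.042). For a two-sided two-sample t-test with n per group, the noncentrality is d·√(n/2). At n = 16 this is 1.04 × √8 = 2.94 on 30 degrees of freedom, and power is 0.812. Sixteen is the smallest n that reaches 0.80. The arithmetic of 11.2 is sound for **one** RCS comparison at 0.05.

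**2. Number of comparisons.** Five outcomes × 2 post-baseline visits = 10 between-hand tests. If QuickDASH is not scored per hand, 4 × 2 = 8. The text does not say which outcomes are scored per hand. The baseline tests (15 in all with them) and the within-group tests (5 outcomes × 2 groups = 10 more) are left out of this count.

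**3. Chance of at least one false positive, independent tests.**
- Either direction: 1 − 0.95^10 = 0.401; 1 − 0.95^8 = 0.337.
- False benefit only: 1 − 0.975^10 = 0.224; 1 − 0.975^8 = 0.183.

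**4. Correlated outcomes and visits.** Simulation under no effect: 16 patients with two hands each, two visits, all outcomes normal (including the counts). The documents give no correlations, so every value here is an assumption. The first column gives the correlation between outcomes / between visits.

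Valid paired tests:

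| Correlation | Ten tests: any | Ten: benefit | Eight tests: any | Eight: benefit |
|---|---|---|---|---|
| 0 / 0 | 40% | 22% | 34% | 18% |
| 0.5 / 0.5 | 32% | 16% | 28% | 14% |
| 0.7 / 0.7 | 25% | 12% | 22% | 11% |

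The independent-samples test that 11.1 actually plans, any direction; each range covers the three rows above:

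| Between-hand correlation | Error per test | Ten tests | Eight tests |
|---|---|---|---|
| 0.3 | 2.1% | 12–20% | 10–16% |
| 0.5 | 0.8% | 5–8% | 4–6% |
| 0.7 | 0.1% | 1% | 1% |

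The second table is lower because both hands belong to one patient. The true variance of the between-hand difference in means is 2σ²(1 − ρ)/n, but the unpaired test uses an estimate of 2σ²/n, so each test is conservative when ρ > 0.

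**5. The look at 8 subjects.** For a single paired RCS endpoint tested at 0.05 with 8 and again with 16 subjects, the error is 8.6% if either result could be reported as the finding. Section 12.1 does not say whether it could, so this is only an illustration.

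**6. Power under the alternatives.** Take 1.92 as the per-hand SD (an assumption). The SD of the within-patient difference is 1.92·√(2(1 − ρ)): 2.72, 2.27 and 1.92 at ρ = 0, 0.3 and 0.5. With n = 16 the noncentrality is 2·√16 divided by that SD: 2.95, 3.52 and 4.17 on 15 degrees of freedom.

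| Between-hand correlation | One paired RCS test at 0.05 | Bonferroni over ten (0.005) |
|---|---|---|
| 0 | 79% | 40% |
| 0.3 | 91% | 60% |
| 0.5 | 97% | 79% |

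**The case against.** The best defence is that RCS is the implicit primary, because 11.2 sizes the trial on nothing else. That gives a reader a lead outcome, but 11.2 does not call it primary, 11.1 and 12.1 treat it as one of five, and no visit is attached. Even if RCS is accepted, two visits remain, each claimable at 0.05 (1 − 0.95² = 9.75% if independent).

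The second defence concerns size. The 25–40% figures belong to paired tests, and the plan specifies independent-samples tests. As written, with a between-hand correlation of 0.5 or more, the overall error is near or below 5%. This is correct and limits what can be said about the error rate. It does not supply a primary test, and the protection is a by-product of ignoring the pairing, which disappears once the hands are analysed as pairs.

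Third, the count could be below eight. Attacks per week might also be recorded per patient, and the case report forms, which were not available for this review, may settle it. With three outcomes scored per hand, six independent paired tests still give 1 − 0.95^6 = 26%.

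Fourth, the favourable rule in 12.1 joins the five outcomes conjunctively, so read literally it needs all five to be better; only the unfavourable rule is met by any one. That makes an early claim of benefit unlikely, but leaves the relation between that look and the final tests unstated.

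Finally, this is a small single-centre study described as preliminary. That tempers the consequence, though naming a primary endpoint costs a small trial nothing.

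**Conclusion.** The concern holds. No efficacy outcome or visit is designated as primary, and 11.1 states a rule under which any of up to ten post-baseline comparisons can be declared significant at 0.05. This follows from the text and depends on no assumed figure.

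The size of the inflation does depend on assumptions: roughly 22–40% with valid paired tests over eight or ten comparisons, and from about 1% to 20% with the planned unpaired test, according to the between-hand correlation. These rest on undocumented correlations and on counts simulated as normal. The firm conclusion is that the planned test cannot be identified; a particular error rate for the plan as written is not established. The sample size calculation is not at fault. The point should be corrected before the analysis.

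**What to change.** - In 8.1 and 11.1, name one primary efficacy endpoint: the between-hand difference in RCS, either at one prespecified visit or as the mean of the 1- and 3-month visits. Either choice meets the objection, and RCS matches the sizing in 11.2.
- Test it with a within-patient (paired) analysis at two-sided 0.05 at the final analysis.
- State which outcomes are scored separately for each hand.
- Make the remaining outcomes and visits secondary, either Holm-adjusted or reported as estimates with confidence intervals and no significance claim.
- Move the text on the end of participation out from under the primary-endpoint heading.
- State how the p<0.05 comparison at 8 subjects in 12.1 relates to the final test, so that the two sections are reconciled.

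The cost is wording only, with no extra patients or visits. A single paired RCS test keeps power at about the planned level or above it, whereas Bonferroni over all ten would lose much of it unless the hands are well correlated. The price is that a positive result on a non-RCS outcome can no longer be claimed at an unadjusted 0.05.
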